Application of Economics & Social psychology to improve Opioid Prescribing Safety (AESOPS) Trial 2 is a multi-site randomized trial that takes place among a clinic organization in Los Angeles, California (AltaMed Health Services) and one in Chicago, Illinois (Northwestern University). Participants in the trial are clinicians. Observations are visits where opioids are prescribed. Clinicians are randomized to receive either: 1) guidelines on opioid prescribing, or 2) information on an opioid harm experienced by one of their patients (non-fatal or fatal overdose). In Los Angeles, fatal overdose letters are already required by the County, therefore, only non-fatal overdose letters will be sent to clinicians in Los Angeles. These will be signed by the County Public Health Officer. In Chicago, Illinois, both types of letters will be sent. Outcomes are milligram morphine equivalents ordered by each participating clinician per week. A secondary outcome is referrals to medication assisted treatment. These data are collected from the electronic health record systems at AltaMed and Northwestern Medical Center. Determining overdoses involves connecting data on overdoses between hospital systems, or in the case of Illinois, state vital records. More specifically, non-fatal overdoses in Los Angeles connect opioid prescribing at AltaMed with Los Angeles County emergency department data (See Appendix 1, Figure 1a), non-fatal overdoses at Chicago's Northwestern University involve a search of the internal database that connects that University's outpatient clinic data with emergency department data (See Appendix 1, Figure 1b), and fatal overdoses among patients at Northwestern connect data from that institution with Illinois State Vital records (Illinois Department of Public Health (IDPH); See Appendix 1, Figure 1c). A pilot study was originally approved for the data exchange in Figure 1c and the secure data sharing exercise was successful.

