1. Clinicians randomized to the overdose notification group will exhibit a greater reduction in weekly MME from the pre- to post-period compared to clinicians randomized to the control group for fatal and non-fatal overdoses.
2. Among the clinicians who prescribed at least one opioid in the study period, those randomized to the overdose notification group will exhibit a greater reduction in the proportion of a clinician's patients prescribed at least 50 daily MME from the pre- to post-period compared to clinicians randomized to the control group for fatal and non-fatal overdoses.

b) Number of subjects:

AltaMed Health Services is a private health system in Los Angeles, California. AltaMed has 35 clinics with 134 clinicians with 17,674 such patients. Clinicians meeting inclusion criteria will be enrolled in the study. Northwestern Medicine is a regional health system affiliated with an academic medical center located in the Chicago region of Illinois and includes 60 primary care clinics that contain 387 clinicians with 12,552 patients using chronic opioid therapy for noncancer pain—on opioids for greater than three months.

c) Mechanism for subject selection or exclusion:

Eligible physicians and patients will be identified using outpatient opioid prescribing data

from electronic medical records. A clinician is eligible for inclusion if: 1) s/he prescribed a qualifying scheduled drug to a patient in the 12 months prior to their fatal or non-fatal overdose 2) the patient is 18 years old or older at the time of the overdose, 3) s/he practices within a health system enrolled in the study, and 4) the overdose occurs during the 12-month observation period.

A patient is eligible for identification in a physician notification if s/he (a) has been prescribed an opioid by an eligible clinician (b) has a documented overdose event in EHR or mortality data. Patients without overdose events will be excluded. Patients with fatal overdoses in Los Angeles County will be excluded to avoid redundancy with existing notification practices.

[figure not shown]
d) Duration of intervention:

The duration of the overdose notification intervention is one day.

e) Total duration which study will be performed (data collection, intervention, and analysis period):

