discontinuation of opioids for persons whose most recent prescription exceeds 49 MME daily dose; or as reported to study staff (10).

If there is a significant difference in the prevalence of these adverse events or overdoses between the treatment and control groups, the differences will be reported to the Data and Safety Monitoring Board and in the publication of the study results. *It is important to note that prior quality evaluations of these letters observed no additional risk of abrupt changes to opioid prescribing upon receipt of a letter (<https://pubmed.ncbi.nlm.nih.gov/30093595/>).*

- Management of overdose and prescribing data poses no more than minimal privacy risks. USC, health systems and IDPH comply with all local and federal security regulations protecting privacy. Identified patient data will be destroyed after the notifications have been prepared. A HIPAA Limited Data Set that includes outpatient prescribing records, overdose events, and notification status will be transferred to USC for data analysis in USC's HIPAA compliant enclave.

b) Experimental Procedures:

Randomization and Allocation. Overdose clusters are the units of randomization in this study. A cluster consists of all clinicians who prescribed one or more of the included scheduled drugs to the patient in the year prior to the overdose. Overdose clusters will be randomized to the overdose notification group or the control group, stratified by the health system which defines the cluster in the year prior to the overdose event.

Allocation will be concealed until after the study groups are assigned. Clinicians who practice at multiple clinics will be assigned to the clinic at which the majority of their visits occurred in the year prior to the overdose event. If clinicians belong to more than one cluster (have multiple patients with opioid-related overdoses), they will be randomly assigned to one of those patients and placed in the corresponding study group. If clinicians belonging to more than one cluster are randomized to the intervention group, they will only receive an overdose notification regarding the one patient to whom they were randomly assigned.

Intervention. Clinicians in the intervention group receive a letter notifying them of their patient's fatal or non-fatal overdose. As described above, we will identify overdoses from electronic health record data from emergency departments and state vital records.

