If randomized to the overdose notification group, physicians who prescribed a qualifying prescription to the deceased or surviving patient in the year prior to their overdose will be informed of the overdose via letter. The letters will alert prescribers to the patient's opioid-related overdose, recommend the use of their state's PDMP, and list evidence-based interventions to lower opioid-related overdoses (Appendix 2 and 3).

Controls. Clinicians in the control group will receive guideline education in the form of the CDC pocket guide and no notification of a patient overdose event (See Appendix 5). https://www.cdc.gov/drugoverdose/pdf/TurnTheTide_PocketGuide-a.pdf

D. Statistical Analysis Plan

Patients who experienced an opioid overdose will be randomized to either the letter intervention or control. We will analyze how the prescribing behavior of those patients' clinicians changed pre-to-post intervention. We will use means and medians for continuous measures for sample descriptive statistics, frequencies for count data and standard deviations, and interquartile ranges for variance. We will evaluate changes in opioid prescribing rates by group using an intent-to-treat difference-in-differences regression model on clinician hydrocodone morphine equivalent weekly dose. The coefficient for the group assignment, overdose type, and time interaction, also known as the difference-in-differences estimator, denotes the change over time in 5 MME hydrocodone pills for prescribers in the intervention group compared to prescribers in the control group for both fatal and nonfatal overdose victims. The use of a mixed-effects hierarchical knotted spline Poisson regression model offers a flexible way to accommodate non-linear trends in prescribing by group before and after introducing the intervention. This model places a knot at the intervention start date allowing slopes before and after the introduction of the intervention to vary for each group. Our primary outcome is the daily average number of 5 MME hydrocodone pills. If we have an excess of data clustering at zero, indicating weeks during which a physician wrote no opioid prescriptions, we will use a zero-inflated or left-censored regression. The regression model estimating the association between letter assignment and weekly 5 MME hydrocodone pills prescribed is shown in Eq. 1:

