$$(pills)_{ijk}^* = \beta_1 + \beta_2 Time_{ij} + \beta_3 (Time_{ij} - t^*) + \beta_4 Group_i + \beta_5 Overdose Type_k + \beta_6 Group_i * Overdose Type_k + \beta_7 Time_{ij} * Group_i + \beta_8 (Time_{ij} - t^*) * Group_i + \beta_9 Time_{ij} * Overdose Type_k + \beta_{10} (Time_{ij} - t^*) * Overdose Type_k + \beta_{11} Time_{ij} * Group_i * Overdose Type_k + \beta_{12} (Time_{ij} - t^*) * Group_i * Overdose Type_k + \eta + \delta_{i(k)} + error$$

where $(pills)_{ijk}^*$ denotes the dependent variable for clinician i in week j , $Time_{ij}$ is the study week indexed by j , t^* is the spline knot for the start of the intervention, $(Time_{ij} - t^*)$ is a truncated line function that is equal to $(Time_{ij} - t^*)$ when $Time_{ij} > t^*$ and 0 otherwise to allow for nonlinear trends in prescribing following the intervention, $Group_i$ is dichotomous for the overdose notification intervention group, $Overdose Type_k$ is dichotomous for a fatal overdose, η is the clinic random effect, and $\delta_{i(k)}$ is the random effect for each clinician i who prescribed to patient k who suffered an overdose.

The mixed logistic regression model for our secondary outcomes is shown in Eq. 2:

$$(high dose Rx)_{ijk} = \beta_1 + \beta_2 Time_{ij} + \beta_3 Group_i + \beta_4 Overdose Type_k + \beta_5 Group_i * Overdose Type_k + \beta_6 Time_{ij} * Group_i + \beta_7 Time_{ij} * Overdose Type_k + \beta_8 Time_{ij} * Group_i * Overdose Type_k + \eta + \delta_{i(k)} + error$$

where $(high\ dose\ Rx)_{ijk}$ is whether the visit had a high dose prescription of 50 MME or greater (yes vs. no) for clinician i , $Time_{ij}$ is the study period (pre- vs. post-intervention) indexed by j , $Group_i$ is dichotomous for the overdose notification intervention group, $Overdose\ Type_k$ is dichotomous for a fatal overdose, η is the clinic random effect, and $\delta_{i(k)}$ is the random effect for each clinician i who prescribed to patient k who suffered an overdose. We will compute the estimated pre- to post-intervention change in the mean proportion of high dose patient visits for each of the four intervention groups: nonfatal control, nonfatal letter, fatal control, fatal letter. The proportion will be calculated by dividing the total number of patient visits where an opioid of at least 50 MME was prescribed by the total number of opioid prescriptions.

E. Privacy of Individuals and Confidentiality of Data

We will utilize two types of data for this study:

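### Eq. 1 and Eq. 2 hold the change over time fixed across clinicians and overdose clusters and name no cluster-robust variance, so letter-effect standard errors are too small if true change varies

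*Combined protocol and SAP*

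**What the plan says.** **Allocation (Section C.b, Randomization and Allocation).** The unit is explicit: "Overdose clusters are the units of randomization in this study". Its content is also explicit: "A cluster consists of all clinicians who prescribed one or more of the included scheduled drugs to the patient" in the year before the overdose. A clinician who belongs to several clusters is tied at random to one patient. "Overdose clusters will be randomized to the overdose notification group or the control group, stratified by the health system which defines the cluster".

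**Models (Section D).** The primary analysis is announced as follows: "The use of a mixed-effects hierarchical knotted spline Poisson regression model". Both equations carry the same two random terms. One is a clinic effect. The other, written with the subscript i(k), "is the random effect for each clinician i who prescribed to patient k who suffered an overdose". Neither is multiplied by time. Slopes differ only through the fixed factors, group and overdose type. A zero-inflated or left-censored model is held in reserve if zeros are frequent.

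**Estimator and hypotheses.** Section D labels one quantity as the effect: "The coefficient for the group assignment, overdose type, and time interaction, also known as the difference-in-differences estimator". The first hypothesis in Section B.a is a different comparison: clinicians sent letters "will exhibit a greater reduction in weekly MME from the pre- to post-period compared to clinicians randomized to the control group".

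**Sites.** The Study Synopsis says "only non-fatal overdose letters will be sent to clinicians in Los Angeles", and Section B.c excludes fatal overdoses in Los Angeles County. Chicago contributes both types.

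**The concern.** The estimand is a change over time, compared between randomised clusters. A random intercept absorbs stable differences in prescribing level. It does not absorb differences in how much clinicians change. If those exist, the model treats each clinician's many weeks or visits as independent information about the letter effect, and the standard error reflects only sampling noise within clinicians. Co-prescribers to one patient also share an allocation, so any correlation between their changes is a further component left out. At stake is a false-positive letter effect, or an interval that is too narrow, for both the weekly pill outcome and the high-dose outcome.

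The secondary concern is that the coefficient named as the estimator compares fatal with non-fatal letter effects. One side of that comparison comes from Northwestern alone and the other from both systems, with no health-system term in either equation.

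**Working it through.** The documents give no alpha, power, variance, intracluster correlation, cluster size or pill volume, so there is no planned figure to reproduce. The reading of the equations decides the main point. The numbers below only illustrate it.

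**1. Terms available for change over time**

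| Source of variation in change | Eq. 1 | Eq. 2 |
|---|---|---|
| Group, overdose type (fixed) | yes | yes |
| Clinician | no (intercept only) | no (intercept only) |
| Overdose cluster, patient k | no | no |
| Clinic | no (intercept only) | no (intercept only) |
| Robust variance named | no | no |

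The subscript i(k) and the word hierarchical may hint at nesting in patient k. The definition, however, gives one effect per clinician, and a patient-level intercept would still not let change vary.

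**2. Approximate size as a function of unknowns.** Let r be the between-clinician variance of true change divided by one clinician's sampling variance, m the clinicians per cluster, and ICC the correlation of true change within clusters. With equal volumes, the true variance over the model-based variance is V = 1 + r[1 + (m − 1)ICC], and the actual error of a nominal 5% test is 2[1 − Φ(1.96/√V)].

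- r = 0: V = 1, error 5.0%.
- r = 0.5, m = 1: V = 1.5, error 11.0%.
- r = 0.5, m = 5, ICC 0.20: V = 1.9, error 15.5%.
- r = 1, m = 1: V = 2, error 16.6%.
- r = 1, m = 5, ICC 0.20: V = 2.8, error 24.2%.

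**3. Simulation of random-intercept fits** (assumed: 200 clinicians, no letter effect, one overdose type, no clinic effect, unequal volumes, no overdispersion, 2,000 runs per setting; ICC 0.20 for m of 2 and 5). Type I error at m = 1 / 2 / 5:

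| r | Poisson slope change by group | Logistic time by group |
|---|---|---|
| 0 | 5.0 / 4.6 / 4.4% | 4.6 / 5.0 / 5.0% |
| 0.5 | 11.7 / 14.4 / 17.6% | 12.2 / 13.8 / 16.5% |
| 1 | 20.3 / 22.8 / 25.1% | 19.3 / 18.6 / 26.4% |

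Monte Carlo error is about 0.5 points near 5% and 0.9 points near 20%. For r above 0, Poisson model standard errors fall short by 1 − 0.0304/0.0386 = 21% up to 1 − 0.0304/0.0531 = 43%. Cluster-robust errors with a G/(G − 1) factor and G − 2 degrees of freedom (G = number of clusters) gave 4.4% to 6.0% throughout.

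A second simulation of the Eq. 1 slope term used other assumptions: 50 or 150 clinicians per arm, clusters of 3, ICC 0.3, 5 or 50 pills a week, and an SD of log change of 0.1 to 0.4 at 26 weeks after the knot. It gave about 5% with no variation and 8% to 73% otherwise. The spread between the two sets shows how little the size is known.

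**4. What r = 0.5 means.** For 26 + 26 weeks with a central knot, the Poisson sampling variance of the change at post-week 26 is 24/(26μ) = 0.923/μ, where μ is pills per week. The SD of true change is then √(0.5 × 0.923/20) = 0.152 at 20 pills, or √(0.5 × 0.923/200) = 0.048 at 200 (both volumes assumed). If a fitted dispersion term multiplied the variance by 5, these become 0.34 and 0.11; by 10, 0.48 and 0.15.

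**5. Site.** Let w be the Los Angeles share of the non-fatal data, and E_NW and E_LA the letter effects. With no true overdose-type effect, the fatal effect is E_NW and the pooled non-fatal effect is w·E_LA + (1 − w)·E_NW. The difference is w(E_NW − E_LA). Fitting the fixed part of Eq. 1 to expected counts with E_NW = −0.10, E_LA = 0 and w = 0.257 gave −0.027, against −0.026 from the formula. A site difference in background trend alone gave about 0.

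The share w is not stated. Section B.b offers two rough proxies, with an assumed 0% to 50% of Northwestern in fatal clusters:

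- Clinicians: 134/521 = 26% to 134/(134 + 193.5) = 41%.
- Patients: 17,674/30,226 = 58% to 17,674/(17,674 + 6,276) = 74%.

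An assumed 10-point site difference in the letter effect would thus show as 2.6 to 7.4 points.

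**The case against.** **Most of the inflation is not about clusters.** In the simulations it is already present with one clinician per cluster; correlation adds about 2 to 7 points, and nothing detectable in one logistic cell (19.3% at m = 1, 18.6% at m = 2). This stands. A reader might infer that ignoring the randomised unit is by itself the main error. The documents do not support that, since cluster sizes are not given and tying each clinician to one patient can only shrink clusters. Inference at the randomised cluster nevertheless covers both components.

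**The percentages rest on assumptions.** This also stands. The direction follows from the equations, and only if true change varies. The printed error term in Eq. 1 might absorb overdispersion, in which case a given r needs more variation in true change. Neither that term nor the reserve models were simulated. The reserve models do not by themselves add varying change.

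**The site point is narrow.** Bias needs the letter effect itself to differ by site. Stratified allocation largely protects against differing background trends, and the clinic intercept absorbs differences in level. A reader might infer that the Section B.a hypotheses are confounded with site. They are not: letter versus control within an overdose type is compared under stratified randomisation. Section D also already promises pre- to post-intervention changes for all four groups on the high-dose outcome.

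**Conclusion.** The main point holds by reading Section C.b against Section D: neither equation lets change over time vary by clinician or overdose cluster, and no variance estimator makes up for it. Standard errors for the letter effect are too small if clinicians' true change varies, and can be smaller still relative to the truth if co-prescribers' changes are correlated. If true change does not vary, there is no inflation. It would go too far to say that the trial's error rate is known to be inflated, or by how much; every percentage above is an illustration on assumed values.

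The site point is secondary and conditional. The three-way coefficient partly reflects site only if the letter works differently in the two systems. That is plausible, because the Los Angeles letters are signed by the County Public Health Officer and the Northwestern templates by a medical director or similar role, but the documents give no evidence on it.

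The change should be made before analysis; confidence in the practical size is moderate at best.

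**What to change.** - State whether δ_i(k) is a clinician effect or a clinician effect nested in patient k.
- In both models, and in any zero-inflated or left-censored replacement, base inference on patient k. Use cluster-robust standard errors with a small-sample correction, or add clinician-by-time and cluster-by-time random effects (the latter was not simulated). The correction matters: without it, the second simulation still gave about 7% to 10% with about 17 clusters per arm.
- Prespecify letter versus control within each overdose type as a model-based pre- to post-period contrast matching Section B.a. In Eq. 1, β8 (non-fatal) and β8 + β12 (fatal) are differences in slope change and should be labelled so. For non-fatal clusters, the group difference between pre-week s and post-week t on the model scale is β7(t − s) + β8(t − t*), so β8 alone is not the hypothesised reduction. In Eq. 2 the contrasts are β6 and β6 + β8.
- Estimate fatal versus non-fatal within Northwestern, or add health system with its time, group and group-by-time interactions (both slopes in Eq. 1). In the latter case, prespecify how the non-fatal letter effect is pooled over systems.
- Report clusters and clinicians per cluster by system and overdose type.

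**Cost.** This is SAP wording only; Section B.f assigns patient and prescriber study identifiers and keeps study identifiers for analysis. Intervals will be wider where change varies. With 40 clusters (38 degrees of freedom) the critical value is 2.02 instead of 1.96. For the Northwestern-only contrast, with equal variances and an assumed fraction f of Northwestern in fatal clusters, the standard error ratio to the pooled contrast is √{[1/(N(1−f)) + 1/(Nf)] / [1/(L + N(1−f)) + 1/(Nf)]}, where N and L are the Northwestern and Los Angeles counts. For f = 0.1 to 0.5 this gives 1.01 to 1.12 on clinician counts and 1.03 to 1.26 on patient counts, so about 1% to 26% larger.

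### Randomisation is stratified by health system, but Eq. 1 and Eq. 2 leave health system and its time trend out; if the two systems' trends differ, the letter-versus-control contrast loses precision and its standard error need not match its true variation

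*Combined protocol and SAP*

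**What the plan says.** Section C.b (Randomization and Allocation) states: "Overdose clusters are the units of randomization in this study". A cluster is every clinician who prescribed to one overdose patient in the preceding year, so clusters differ in size. Allocation is "stratified by the health system which defines the cluster in the year prior to the overdose event". No other stratification factor is named, and neither an allocation ratio nor a blocking scheme is given.

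Section D writes both models out term by term. Eq. 1 has time, a spline term after the letter date, group, overdose type and their interactions. Eq. 2 has the same structure with a pre/post period and no spline. Each adds two random intercepts: "η is the clinic random effect", and a second that "is the random effect for each clinician i who prescribed to patient k who suffered an overdose". The text describes the knot as "allowing slopes before and after the introduction of the intervention to vary for each group"; the equation also lets slopes vary by overdose type. Health system appears in neither equation, alone or with time, and no analysis by system is planned elsewhere.

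The letter effect is a change over time: "The coefficient for the group assignment, overdose type, and time interaction, also known as the difference-in-differences estimator".

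Section B.b gives system totals, not enrolled numbers: "AltaMed has 35 clinics with 134 clinicians with 17,674 such patients", and Northwestern "includes 60 primary care clinics that contain 387 clinicians with 12,552 patients".

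**The concern.** A factor that restricts the randomisation would normally appear in the analysis, so that the model matches the design and its contribution is removed from the error. Here what matters is trend, because the effect is measured as change. Among clinicians with a non-fatal overdose patient, the models impose one secular trend on both systems.

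There are reasons to doubt a common trend. The systems are in different states, one being a clinic organisation and the other affiliated with an academic medical center. Only Los Angeles already mandates fatal-overdose letters. The stated patient loads differ about fourfold (17,674/134 = 132 per clinician against 12,552/387 = 32). None of this measures a trend difference, but it makes equality something to allow for rather than assume.

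Stratification balances the number of clusters per arm within a system, not the number of clinicians. A few large clusters can tilt one arm toward one system, and that system's trend then adds noise to the arm difference. At stake are precision and a standard error that reflects the real sampling variation.

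**Working it through.** The plan states no sample size, power, effect size or SD, so there is no planned figure to reproduce. All inputs below are assumptions unless a source is given.

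**1. Level differences do no harm.** A Gaussian random-intercept stand-in for Eq. 1 was simulated with 134 + 387 = 521 clinicians (Section B.b totals), 52 weeks, a knot at the letter date and 600 runs. With a pure level difference of 2 residual SDs between systems, the model SE of the group-by-spline coefficient (β8) was 3.68e-3 with or without the system terms.

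**2. Trend differences, clinicians allocated singly.** Let D be the difference between systems in pre-to-post change, in SDs of clinician change, and p the AltaMed share. Omitting system-by-time multiplies the reported SE by √(1 + p(1−p)D²). With p = 134/521 = 0.257, p(1−p) = 0.191:
- D = 0.25: √1.012 = 1.006
- D = 0.5: √1.048 = 1.024
- D = 1.0: √1.191 = 1.091

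This understates the issue, because the trial randomises clusters.

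**3. Trend differences, clusters allocated.** Assume 30 Los Angeles and 60 Northwestern clusters, mean size 3, 1:1 within system, SD of clinician change σ = 0.30 log units, within-cluster correlation 0.05. Clinician change is regressed on arm with cluster-robust SEs (3,000 trials). A system difference Δ gives D = Δ/0.30.

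| Δ | D | Reported SE, without/with system | True variance, without/with | Null rejection without system |
|---|---|---|---|---|
| 0.1 | 0.33 | 1.06 | 1.04 | 5.2% |
| 0.2 | 0.67 | 1.19 | 1.14 | 3.5% |
| 0.3 | 1.00 | 1.39 | 1.33 | 2.8% |

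A repeat gave the same SE ratios, with variance ratios 1.04, 1.18, 1.36. With Δ = 0 the SE ratio was 1.006.

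A hand check: let K be the ratio of mean squared cluster size to mean size, and p = 30/90, so p(1−p) = 0.222. The squared SE ratio is about 1 + 0.222·D²·K/(1 + 0.05(K−1)). Solving 1.389² = 1.929 at D = 1 gives K ≈ 5, that is, a size variance v = 3K − 9 ≈ 6. The same K gives 1.05 and 1.19 at the smaller differences.

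For the true variance, each arm has 15 + 30 clusters and 135 clinicians. Chance imbalance adds a fraction D²·v·[(2/3)²·15 + (1/3)²·30]/[135·(1 + 0.05(K−1))] = D²·v·10/162 = 0.37·D² at v = 6. That is 4%, 16% and 37%, close to the simulated values. The formula also shows that the loss vanishes if all clusters are the same size (v = 0) and allocation within systems is balanced.

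**4. Closer to the planned likelihood.** Pre/post Poisson counts were fitted conditionally on each clinician's total, as a stand-in for the random intercept, with the same clusters. Across the settings tried, the true variance without system exceeded that with it by 3–8%, 22–30% and 34–59% at Δ = 0.1, 0.2 and 0.3, with no loss at 0. The reported SE hardly moved (ratios 0.997, 0.996, 0.995 in one run), because a Poisson model has no free residual variance to take up the omitted trend. With an assumed median of 26 per period and no other overdispersion, the unadjusted SE was 0.87 and 0.75 of the true SD at 0.2 and 0.3. False positives across checks were about 9–16%, and adding system restored about 5–6%.

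**The case against.** A reader might infer that the contrast is imprecise and its standard error wrong as a matter of fact, or that the error is conservative and the only cost is power. The documents support neither. Both consequences need a trend difference that the plan does not quantify. The conservative direction comes from cluster-robust errors, which Section D does not mention. It specifies a mixed-effects Poisson model, with a zero-inflated or left-censored alternative, and under a Poisson stand-in the model-based error is too small when trends differ.

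Nor should the mechanism be read as bias. Under randomisation the imbalance is chance, with zero expectation.

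The size is also open to challenge. A difference of 0.3 log units is a full assumed SD of clinician change and means a relative difference of e^0.3 = 1.35 between systems across two six-month windows; 0.1 means e^0.1 = 1.11 and costs little. Cluster-size spread matters as well. Another run of the linear design gave excess variance of about 1%, 7% and 13%; by the formula above, 13% at D = 1 corresponds to v ≈ 2 instead of 6. In the Gaussian stand-in with balanced single-clinician allocation and a trend difference of 0.5 residual SD, the model SE of β8 changed by about 1% (3.71e-3 against 3.67e-3). Fatal overdoses enter only from Chicago, so the Overdose Type terms carry part of any system trend, although they cannot separate the systems among non-fatal overdoses.

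Finally, with larger assumed counts (median about 200 per period) and clinician changes varying with SD 0.30, null rejection in the Poisson stand-in was about 72–76% with or without the system term. That stands as a warning that this fix does not repair the standard error in general. It comes from unmodelled clinician slope variation, a different problem, and it does not cancel the precision gained by modelling the stratum's trend.

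**Conclusion.** The point holds in conditional form. The sole stratification factor is absent from both models, and nothing in them lets the two systems' trends differ among non-fatal overdoses. If the trends coincide, nothing is lost. If they differ, the contrast is less precise by an amount that rises with the square of the difference and with the spread in cluster size: about 3–8% in variance at 0.1 log units and about 35–60% at 0.3 under the assumed Poisson inputs, and as little as 13% at 0.3 in the linear run with the smallest loss. The mismatch of the reported standard error has no fixed sign: too large with cluster-robust errors, too small with the planned model's own.

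These figures rest on assumed cluster numbers, sizes, SD, correlation and 1:1 allocation within system, and on simplified stand-ins for Eq. 1. They were not computed for the logistic Eq. 2, where the omission is the same. This is a free improvement in the analysis; no validity failure has been shown.

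**What to change.** In Section D, add health system as a fixed effect to both models. In Eq. 1 add its interactions with Time and with (Time − t*); in Eq. 2 add its interaction with the pre/post period. Keep the clinic and clinician random effects. If the terms are left out, the SAP should say why. It should also name the method for standard errors, because the direction of any mismatch depends on it.

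The cost is one sentence in the SAP, three coefficients in Eq. 1 and two in Eq. 2. Each system prepares its own analysis data set, so membership is known for every clinician and no new data are needed. If trends turn out to be common, the added terms cost almost nothing in precision. Clinician-level slope variation and correlation within overdose clusters need their own treatment.
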